6.4 Reporting to the Ethics Committee

The sponsor will assess whether any relevant safety information that becomes available during the study should be reported ad hoc to the EC.

The sponsor has the obligation to, once a year throughout the clinical trial (or on request), submit a progress report to the EC containing an overview of all SARs (Serious Adverse Reactions) occurred during the reporting period and taking into account all new available safety information received during the reporting period.

All deaths until 48h after the study period will be reported without delay to the Sponsor (irrespective of whether the death is related to disease progression, study procedure or is an unrelated event). The

sponsor will notify all deaths, as soon as possible after becoming aware, to the Central EC and provide additional information if requested.

7 Statistics and Data Analysis

7.1 Sample Size

The study is powered to detect a 0.22 mM within-patient increase in plasma 3HB with 95% certainty, 80% power, calculated with a paired t-test. The anticipated effect size is 0.786 given that patients not treated with ketone esters have a mean difference of 0.001mM between intervention day I and 2 with a SD of 0.28mM (based on prior data from ICU patients) and the anticipated required increase with the administration of ketone esters is 0.22mM (which was the effective increase in the mice studies). If the lower limit of the 95% confidence interval is not above 0.22mM increase, a higher dose will be tested.

Approximately 160 participants will be screened to achieve 16 participants completing the 48h study period or an estimated total of 8 evaluable participants per treatment group.

The screening will be repeated for each dose study. In total a maximum of approximately 480 patients will be screened and a maximum of 3x 16 patients completing the 48h study period will be included.

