We will first perform this trial with a 25 g dose of 3HHB divided over 6 boluses. The density of 3HHB is 1.07 g/ml, 25 g has a volume of 23.4 ml, so each bolus consist of 3.9 ml 3HHB. Next, we will assess the primary and secondary endpoints in this cohort of patients. If the dose of 25 g is found safe but ineffective for increasing plasma 3-hydroxybutyrate at least with 0.22 mmol/l, a second cohort of patients will be tested with the same cross-over study design but with a higher 3HHB dose (50 g of 3HHB, divided over 6 boluses of 7,8 ml). If this dose is again safe but ineffective, a third cohort of patients will be tested with the same cross-over study design with an increased dose of 75 g of 3HHB, divided over 6 doses of 11.7ml. For each cohort of patients tested (cohort I to test 25 g, cohort 2 to test 50 g and cohort 3 to test 75 g),

16 patients will be included. If a patient is not able to complete the 48h study period (e.g. due to consent withdrawal or due to unplanned surgery or other procedures) and this is not related to safety concerns that are directly attributed to the intervention, an extra patient will be included in order not to compromize the statistical power of the study.

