7.2 Statistical Analysis

For each patient, and for each study day, maximum concentration, time to reach maximum concentration, delta Max (difference between maxium concentration and baseline concentration), area under the curve, elimination rate and elimination half life will be calculated for 3HBB and its metabolites 3-hydroxybutyrate and 1,3-butanediol. Delta Max of 3-hydroxybutyrate and time within range (plasma 3-hydroxybutyrate 0.22mmol/l above baseline value) will be calculated as primary outcome variables. For blood lipid parameters, maximum concentration, time to reach maximum concentration, delta Max (difference between maximum concentration and baseline concentration), and area under the curve will be calculated. Data will be compared with paired t-tests after transforming the data to near-normally distributed values if needed. If the latter is not possible, non-parametrical tests will be used. Within the crossover design, each patient thus serves as his/her own control.

To investigate whether the order of administration of placebo and 3HHB affected the response, the delta Max of the placebo day and the 3HHB day will be assessed with a repeated measures ANOVA in which the grouping variable will be randomization (placebo/3HHB or 3HHB/placebo) and time is the difference between test day I and test day 2.If more than one dose will be tested, parameters will also be compared between doses. These data will be compared with standard t-tests after transforming the data to near-normally distributed values if needed. If the latter is not possible, non-parametrical tests will be used. P-values will be considered significant when at or below 0.05 without correction for multiple testing. If a higher dose reached a significant increase in the paired analysis, and also compared to the lower dose, this will further strengthen the conclusion that the lower dose was ineffective while the higher dose was effective. If the higher dose does not reach a statistical difference from the lower dose this might suggest that the lower dose already created a small, but non-statistical increase which was not picked-up in the paired analysis.

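### The 80% power in section 7.1 is for a test against zero, but the dose decision needs the lower 95% limit above 0.22 mM, so the stated power does not apply to it

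*Protocol*

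**What the plan says.** Protocol section 7.1 gives the basis for 16 completers per dose: "The study is powered to detect a 0.22 mM within-patient increase in plasma 3HB with 95% certainty, 80% power", from a paired t-test. It adds that "The anticipated effect size is 0.786". The ingredients are that untreated patients "have a mean difference of 0.001mM between intervention day I and 2 with a SD of 0.28mM", and that "the anticipated required increase with the administration of ketone esters is 0.22mM".

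The same paragraph ends with the decision rule: "If the lower limit of the 95% confidence interval is not above 0.22mM increase, a higher dose will be tested".

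Two other places bear on whether a dose counts as effective. Section 2.4 moves to the next cohort "If the dose of 25 g is found safe but ineffective for increasing plasma 3-hydroxybutyrate at least with 0.22 mmol/l", with no confidence limit or test named. Section 7.2 compares the 3HHB and placebo days by paired t-test, takes p-values at or below 0.05 as significant, and judges doses by whether the paired comparison was significant: "If a higher dose reached a significant increase in the paired analysis". It mentions no null value other than the usual zero.

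**The concern.** In section 7.1 the figure 0.22 mM plays two roles that do not fit together. In the power calculation it is the assumed true effect, measured from a null of zero. In the decision rule it is the value that the lower confidence limit must clear, so it is itself the null. A trial sized to tell 0.22 from zero is not thereby sized to show that an increase exceeds 0.22.

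The rule in 7.1 governs whether a further 16 ICU patients are enrolled at a higher dose. It also governs how the primary objective is answered. A reader of 7.1 would take it that a dose delivering the target increase has an 80% chance of being accepted. Under the rule as written that chance is a few per cent. Section 7.2 would meanwhile usually describe the same cohort as showing a significant increase, so the protocol could yield two opposite statements about one dose.

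**Working it through.** **Inputs, all from section 7.1.** Assumed true increase 0.22 mM; SD 0.28 mM for the day 1 to day 2 difference in untreated patients; untreated mean difference 0.001 mM; 16 completers, each receiving both treatments; 95% confidence. Sidedness is not stated. Two-sided is the base case and one-sided is shown beside it.

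**Step 1: reproduce the plan's figure.** Effect size = 0.22/0.28 = 0.786, as stated. For a two-sided paired t-test against zero with n = 16, the noncentrality is 0.786 × √16 = 3.14 and the critical value on 15 degrees of freedom is 2.131. Power from the noncentral t distribution is 77.6% at n = 14, 80.8% at n = 15 and 83.6% at n = 16. The smallest n for 80% is 15, and 16 is the next even number. Subtracting the 0.001 mM (0.219/0.28 = 0.782) still gives 15. The sample size is therefore right for a test against zero.

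**Step 2: the rule as a test.** The lower limit is mean − 2.131 × s/√16. Requiring it to exceed 0.22 is a t-test of the increase against 0.22. With s = 0.28 the standard error is 0.28/4 = 0.070 and the half-width is 2.131 × 0.070 = 0.149. The observed mean must therefore exceed 0.22 + 0.149 = 0.369 mM.

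**Step 3: probability of meeting the rule.** This is P(T > 2.131), where T is noncentral t on 15 degrees of freedom with noncentrality (true increase − 0.22)/0.070.

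| True increase (mM) | Noncentrality | Rule met, two-sided 95% CI | Rule met, one-sided 95% bound |
|---|---|---|---|
| 0.22 | 0 | 2.5% | 5.0% |
| 0.25 | 0.43 | 6.0% | 10.8% |
| 0.30 | 1.14 | 18.7% | 29.0% |
| 0.35 | 1.86 | 41.2% | 55.1% |
| 0.40 | 2.57 | 67.2% | 79.0% |
| 0.43 | 3.00 | 80.1% | 88.8% |
| 0.44 | 3.14 | 83.6% | 91.2% |

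A simulation of 400,000 cohorts at a true 0.22 mM met the two-sided rule in 2.51%. The last row shows the mismatch directly: the rule has the power found in Step 1 only when the true increase is 0.22 + 0.22 = 0.44 mM, twice the target.

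**Step 4: sensitivity to the SD.** An 80% probability needs a noncentrality of about 3.00, that is, a true increase of 0.22 + 3.00 × SD/4. This is 0.43 mM at SD 0.28. Over an assumed range of half to one and a half times that SD, it is 0.325 mM at SD 0.14 and 0.535 mM at SD 0.42.

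**Step 5: sections 7.1 and 7.2 on the same data.** A lower limit above 0.22 is also above zero, so every cohort that meets the rule is significant against zero. At a true increase of 0.22 mM and SD 0.28, 83.6% − 2.5% = 81.1% of cohorts would be significant in the paired test and still fail the rule in 7.1.

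**The case against.** The strongest reply is that the rule is deliberate. The objective is a dose that raises 3-hydroxybutyrate by at least 0.22 mmol/l, and asking for confidence that the increase exceeds that value is coherent and conservative. On that view the 2.5% at a true 0.22 mM is simply the rule's type I error: it follows from the definition of a 95% interval, whatever n or SD, and is no fault. This stands as a defence of the rule. It does not defend attaching the 80% to it.

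Second, the true increase may be well above 0.22 mM, and the rule does well at 0.43 and beyond. That is possible, but the protocol anticipates no larger value, and a larger response would not make the stated calculation apply.

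Third, the SD of 0.28 mM describes day-to-day change in untreated patients, whereas the primary variable in 7.2 is delta Max, compared between a 3HHB day and a placebo day. This is fair. Every figure above other than the 2.5% (or 5%) at 0.22 mM depends on that SD, hence the range in Step 4.

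Fourth, the sentence in 7.2 is about interpreting differences between doses and is not an escalation rule. That is true, but it does use paired significance to label doses effective or ineffective, so it competes with 7.1.

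The point is not one that can be left to the SAP. The protocol itself states both the power and the rule, and they conflict.

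**Conclusion.** The point holds as an inconsistency between the basis of the power statement and the decision rule. The 80% in 7.1 belongs to a test against zero, the decision in 7.1 is a test against 0.22 mM, and nothing else in the protocol reconciles them. At a true increase of exactly 0.22 mM the rule is met in 2.5% of cohorts (5% with a one-sided bound), assuming approximate normality. With 16 patients and SD 0.28 mM it reaches 80% only at about 0.43 mM, or about 0.33 to 0.54 mM for SDs of 0.14 to 0.42. A dose that only just reaches the target would nearly always be judged not shown effective. If safe, and if it is not already the highest dose, it would be followed by a higher-dose cohort.

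Four stronger readings are not supported:

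- A reader might infer that the sample size is miscalculated. It is not: 16 reproduces for a test against zero.
- A reader might infer that the trial would give the wrong answer to its primary objective. Failing the rule means that an increase above 0.22 mM was not demonstrated, which is not the same thing. Near-certain failure also applies only close to 0.22 mM.
- A reader might take section 2.4 as a further criterion, such as an observed mean of at least 0.22. It names no statistical criterion and can be read as the target that 7.1 puts into operation.
- A reader might conclude that the rule should become a confidence interval excluding zero, since that is where the 80% applies. The protocol does not support this: a dose with a mean increase below 0.22 mM could then count as effective, against the objective in the synopsis and the endpoint in 2.2.

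**What to change.** Reconcile sections 7.1 and 7.2, and the wording in 2.4, so that a single criterion decides whether a dose is effective. Replace the 80% statement with the operating characteristics of that criterion, leaving n unchanged. Which criterion to use is for the sponsor to decide.

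If the present rule is kept, section 7.1 could say: with 16 patients and an SD of 0.28 mM, the lower limit of the two-sided 95% confidence interval exceeds 0.22 mM with probability 2.5% at a true increase of 0.22 mM, 19% at 0.30 mM and 80% at 0.43 mM. It should also say that the SD is taken from untreated patients and is an assumption for delta Max under treatment, and whether the interval is two-sided. Section 7.2 should then make clear that significance against zero does not by itself label a dose effective.

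The cost is wording in three sections and no extra patients. If the current rule stays, the stated power becomes visibly less favourable.

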7.2 Statistical Analysis

For each patient, and for each study day, maximum concentration, time to reach maximum concentration, delta Max (difference between maxium concentration and baseline concentration), area under the curve, elimination rate and elimination half life will be calculated for 3HBB and its metabolites 3-hydroxybutyrate and 1,3-butanediol. Delta Max of 3-hydroxybutyrate and time within range (plasma 3-hydroxybutyrate 0.22mmol/l above baseline value) will be calculated as primary outcome variables. For blood lipid parameters, maximum concentration, time to reach maximum concentration, delta Max (difference between maximum concentration and baseline concentration), and area under the curve will be calculated. Data will be compared with paired t-tests after transforming the data to near-normally distributed values if needed. If the latter is not possible, non-parametrical tests will be used. Within the crossover design, each patient thus serves as his/her own control.

To investigate whether the order of administration of placebo and 3HHB affected the response, the delta Max of the placebo day and the 3HHB day will be assessed with a repeated measures ANOVA in which the grouping variable will be randomization (placebo/3HHB or 3HHB/placebo) and time is the difference between test day I and test day 2.If more than one dose will be tested, parameters will also be compared between doses. These data will be compared with standard t-tests after transforming the data to near-normally distributed values if needed. If the latter is not possible, non-parametrical tests will be used. P-values will be considered significant when at or below 0.05 without correction for multiple testing. If a higher dose reached a significant increase in the paired analysis, and also compared to the lower dose, this will further strengthen the conclusion that the lower dose was ineffective while the higher dose was effective. If the higher dose does not reach a statistical difference from the lower dose this might suggest that the lower dose already created a small, but non-statistical increase which was not picked-up in the paired analysis.

The study setup is designed and will continue until 16 participants per tested dose completed the 48h study period. This is the primary analysis (per-protocol-analysis). Data from patients with a shorter study period will be analysed in as a sensitivity analysis to confirm those partial results are in line with the primary data set. Imputation of missing data would not be accurate due to the small data set.

8 Data handling

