2.4 Trial Design

This will be a single center trial, in adult critically ill patients. With a cross-over design (Fig. 1), patients will receive in random order on 2 consecutive days 3HHB and placebo.

Patients will receive the investigational product between ICU day 4 and 14, to avoid the time of increase in endogenous ketogenesis that we have previously documented to be present in the first 2 to 3 days in ICU [6]. The investigational product (3HHB) or placebo will be delivered through the enteral feeding tube.

Figure 1: Cross-over design of the trial. In group 1, participants will receive 3HHB on intervention day 1, followed by a placebo on intervention day 2. Group 2 will receive placebo on intervention day 1 and 3HHB on intervention day 2. Repetitive blood sampling is indicated in red.

Patients are typically started on enteral nutrition (EN) within 48 hours of admission, unless they are able to eat. EN is delivered for 2x10h per day (8am-6pm and 8pm-6am), with 2x2h interruption (6-8am and 6-8pm) to measure gastric residual volume (Fig 2). EN is usually started at a low rate, and increased depending on tolerance (as deducted in part from gastric residual volumes). For this trial, the caloric intake will be kept constant over the 2 intervention days avoiding the influence of caloric intake on outcome measures. Patients with nasogastric tubes who are not receiving enteral nutrition are also eligible for inclusion. This will allow to study ketone absorption and clearance in both fed and unfed state in the critically ill patient.

Figure 2: 10 hour feeding scheme. Intermittent administration of 3HHB/placebo (in green) every hour for 6 times.

We will administer 3HHB or placebo via repeated small boluses through the nasogastric feeding tube, as is also done for enterally administered medication. The nasogastric tube will be flushed with a 5% glucose solution prior and after administration of 3HBB or placebo to ensure that the bolus has completely entered the stomach while also avoiding clotting of the nasogastric tube.

The first bolus wil be given at 10 am (after 2 hours of enteral feeding) and this wil be repeated 5 times with one hour interval (6 doses in total). After the last bolus, the patient will be fed for three more hours. The next day, this procedure will be repeated (Fig. 1).

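### Area under the curve has no baseline term, unlike delta Max and time within range, so its paired t-test carries avoidable day-to-day noise in 3-hydroxybutyrate and lipids

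*Protocol*

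**What the plan says.** Protocol section 7.2 lists the parameters to be derived for each patient and day. For the ester and its metabolites the list includes "delta Max (difference between maxium concentration and baseline concentration), area under the curve, elimination rate". For lipids it is "delta Max (difference between maximum concentration and baseline concentration), and area under the curve will be calculated". In both places baseline enters delta Max but not AUC, and no time limits are given for AUC.

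The primary variables are both referenced to baseline: "Delta Max of 3-hydroxybutyrate and time within range (plasma 3-hydroxybutyrate 0.22mmol/l above baseline value) will be calculated as primary outcome variables".

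The test is fixed for all parameters: "Data will be compared with paired t-tests after transforming the data to near-normally distributed values if needed". If several doses are tested, parameters are also compared between doses.

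Three other sections bear on this:
- Section 2.4 recognises an endogenous source of 3-hydroxybutyrate. Dosing starts on ICU day 4 "to avoid the time of increase in endogenous ketogenesis that we have previously documented".
- Section 2.5 schedules a sample before the first bolus on each test day, and further samples until 4 am.
- Section 7.1 gives, for untreated patients, a "mean difference of 0.001mM between intervention day I and 2 with a SD of 0.28mM".

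**The concern.** An AUC over the sampled 18 h (10 am to 4 am) contains the patient's own level multiplied by 18 h. If that level differs between the two days, the difference is also multiplied by 18 and enters the 3HHB-minus-placebo contrast. The untreated SD in section 7.1 (0.28 mM) is larger than the target rise (0.22 mM), so this component can be large next to what the supplement adds.

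An illustration, with a flat placebo day for simplicity: the pre-bolus value is 0.30 mM on the placebo day and 0.10 mM on the 3HHB day, and the supplement adds 0.22 mM for the equivalent of 7.5 h.
- Placebo-day AUC: 0.30 × 18 = 5.40 mM·h.
- 3HHB-day AUC: 0.10 × 18 + 0.22 × 7.5 = 3.45 mM·h.
- Difference: −1.95 mM·h, although the supplement added +1.65. Delta Max on the same record is +0.22 against 0.

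At stake is the precision of a secondary summary of exposure. A noisy AUC could disagree with delta Max on the same samples, or blur the comparison between doses, for no better reason than that available baseline information was left out.

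**Working it through.** **The plan's own figure.** Effect size 0.22 / 0.28 = 0.786. A two-sided paired t-test at 5% needs n = 15 for 80% power (80.8%); n = 16 gives 83.6%. The stated 16 is consistent. That calculation concerns the primary increase, not AUC.

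**Inputs from the protocol.** n = 16 per dose (7.1). There are 13 samples per day: hourly from 10 am to 4 pm (7), then two-hourly to 4 am (6), which matches the stated 26 in total (2.5). SD of the untreated between-day difference is 0.28 mM (7.1).

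**Assumptions, not in the protocol.**
- The 0.28 mM is the SD of a difference between two single samples.
- A share s of its variance is a level shift lasting the whole day; the rest is independent sample noise. s is taken from 0.3 to 0.9.
- The rise of 0.22 mM is present from 11 am to 4 pm and falls in a straight line to zero at 8 pm.

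**AUC gain.** The trapezoidal weights (hours) are 0.5; 1 five times; 1.5; 2 five times; 1. They sum to 18 and their squares sum to 28.5. The gain is 0.22 × (5 + 1.5 + 2 × 0.5) = 0.22 × 7.5 = 1.65 mM·h.

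**SD of the between-day difference in AUC.**
- Uncorrected: 0.28 × √V, with V = 18² s + 28.5 (1 − s).
- Covariance factor with the pre-bolus difference: c = 18 s + 0.5 (1 − s).
- With that difference as a covariate: 0.28 × √(V − c²).
- After subtracting 18 h × baseline: 0.28 × √(V − 36 c + 324).

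For s = 0.3: V = 117.15 and c = 5.75. The three SDs are 0.28 × √117.15 = 3.03, 0.28 × √84.09 = 2.57 and 0.28 × √234.15 = 4.29 mM·h.

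**Power at n = 16, two-sided 5%** (noncentral t for the paired tests; simulation of the intercept test for the covariate):

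| s | SD uncorrected (mM·h) | Planned test | Plain subtraction | Covariate |
|---|---|---|---|---|
| 0.3 | 3.03 | 53% | 30% | 63% |
| 0.5 | 3.72 | 38% | 40% | 61% |
| 0.7 | 4.30 | 30% | 60% | 70% |
| 0.9 | 4.80 | 25% | 97% | 97% |

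**Checks.**
- Type I error of the covariate test stays near 5%.
- If nothing persists (s = 0), the covariate costs about one point of power (98% uncorrected, 97.6% adjusted).
- Plain subtraction reduces the SD only when 36 c > 324, that is c > 9, or s above 8.5 / 17.5 = 0.49.
- With a rise of 0.37 mM and the same shape, the planned test has about 93, 80, 68 and 58%, and the covariate test about 97, 96, 99 and 100%.
- Duration matters too. If the whole 0.28 mM is a shift lasting all day, the planned test has 17% power when the 0.22 mM rise lasts 6 h only and 84% when it lasts all 18 h.

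**The case against.** The strongest reply is that the protocol never calls the AUC total. It names the parameter and leaves out baseline, time limits and integration rule, which a statistical analysis plan often supplies. That is fair as far as the definition goes. What stands is that section 7.2 does write baseline into the neighbouring metrics and does fix the test, and a paired t-test on AUC as listed makes no use of the pre-bolus sample.

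The second reply is that little depends on AUC. That also stands. It is not a primary variable and the escalation rule in section 7.1 does not use it. Time within range already measures duration of exposure against baseline.

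The third concerns the assumed rise. Section 7.1 requires a lower 95% limit above 0.22 mM. With SD 0.28 and n = 16 the half-width is 2.131 × 0.28 / 4 = 0.149, so a dose would have to show a mean of about 0.37 mM. At that rise the planned AUC test has 58% to 93% power. The covariate still gains, but less is lost without it.

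A reader might also infer that about a third of true responders would be scored as falling. In the model above, a negative AUC difference does occur in 29% to 37% of patients. But no patient is classified by AUC; the test is on the mean, which would be negative in only 2% to 9% of trials. Delta Max is not immune either: in the same model it is lower on the 3HHB day in 27% of patients at s = 0.3 and 23% at s = 0.5. The fraction depends on the assumed profile and persistence and says nothing about lipids.

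**Conclusion.** The point holds as a loss of precision in a secondary measure. Section 7.2 treats AUC differently from the other level-based metrics, for analytes with an endogenous level, and leaves unused a sample that is drawn on both days. Under the stated assumptions the covariate raises power by about 10 points at a persistent share of 0.3 and about 70 points at 0.9, and costs almost nothing if the level does not persist.

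The size is uncertain. The protocol gives neither the persistent share nor the shape of the rise, and does not say which daily measure the 0.28 mM describes. No lipid variance is given, so for lipids the argument is qualitative only.

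It would be wrong to conclude that level shifts bias the comparison or swamp the supplement's effect. Randomised order makes them noise, and the loss shrinks with larger or longer rises. The primary outcomes and the choice of dose are not in question.

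**What to change.** In section 7.2, for 3-hydroxybutyrate and the lipids, state that AUC is taken over the sampled window of 10 am to 4 am. Analyse the within-patient AUC difference (3HHB day minus placebo day) by regression, with the between-day difference in pre-bolus concentration as covariate. Report the intercept with its 95% confidence interval.

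Do not simply subtract 18 h times the single baseline sample. That multiplies the noise of one sample by 18 and loses power when the level is not persistent (30% against 53% at s = 0.3).

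The cost is one sentence and one degree of freedom, with no new samples or patients. One condition should be stated: the day 2 pre-bolus sample comes 19 h after the last day 1 bolus (3 pm to 10 am), so the adjustment, like delta Max itself, assumes that no effect of day 1 remains by then.

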2.5 Translational research

Blood glucose and 3-hydroxybutyrate concentrations will be quantified repeatedly using blood gas analysis and point-of-care devices during the 48h trial window.

For this trial, we will collect blood samples at 10 ± 1 am on ICU test day I, before administration of the first bolus, repeat this every hour, up to I hour after the last bolus (4 pm), and then every 2 hours until 12h post final bolus (4 am on ICU test day 2). We will repeat this on test day 2. In total, 26 samples (104 ml blood) will be collected from each patient. To minimize blood waste and reduce infection, we will use a VAMP system for blood sampling. Each sample consists of I EDTA tube (purple K2E tube - BD Vactutainer 368861) containing 4 ml of blood. Samples will be stored on ice immediately and processed for further analysis. After processing, samples will be frozen at -20°C and stored at -80°C.

We will collect a urine sample from the 24h urine collection at 8 am ± 1 hours at the end of both intervention days. These samples will be processed, frozen and stored at -80°C for further analysis.

As a standard of care, whole blood glucose measurements are performed every 4 hours on arterial blood using a blood gas analyzer in the ICU. Using the left-over of this clinically collected sample, we will also measure 3-hydroxybutyrate using ketone test strips (Nova StatStrip).

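### Delta Max uses the highest of all 12 post-dose samples of the day minus one pre-dose value, so the paired 3HHB-minus-placebo contrast can understate the rise and may lose precision

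*Protocol*

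**What the plan says.** Protocol section 7.2 computes, for each patient and study day, "delta Max (difference between maxium concentration and baseline concentration". It then states: "Delta Max of 3-hydroxybutyrate and time within range (plasma 3-hydroxybutyrate 0.22mmol/l above baseline value) will be calculated as primary outcome variables". The comparison is fixed too: "Data will be compared with paired t-tests after transforming the data to near-normally distributed values if needed".

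The samples come from section 2.5. The pre-dose sample is taken at "10 ± 1 am on ICU test day I, before administration of the first bolus", and the later ones follow this rule: "repeat this every hour, up to I hour after the last bolus (4 pm), and then every 2 hours until 12h post final bolus". The total is consistent with that: "In total, 26 samples (104 ml blood) will be collected from each patient". Section 2.4 gives six hourly boluses from 10 am, so the last is at 3 pm, and describes enteral feeding "with 2x2h interruption (6-8am and 6-8pm".

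Section 7.1 judges the increase against 0.22 mM: if the lower 95% confidence limit is not above that value, a higher dose is tested. No section limits the samples that may supply the maximum, and none says that the baseline is an average.

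**The concern.** A maximum of noisy values is biased upward, and more so the more values compete for it. Pairing with placebo removes this bias only if it is equally large on both days. On placebo all 12 post-dose samples compete on equal terms. On the 3HHB day, if ketones are raised for only some hours, the maximum comes mainly from those hours. The placebo day then carries the larger upward bias, and subtracting it takes away too much.

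Separately, delta Max subtracts one pre-dose value with a fixed weight of 1 on each day. Any short-term noise in the two baselines passes in full into the contrast.

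Both matter because the contrast is held against a fixed threshold. An estimate that is too low or too imprecise can make an effective dose look ineffective and open another cohort of 16 patients.

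**Working it through.** **Sampling.** After the pre-dose sample: 11 am, noon, 1, 2, 3, 4, 6, 8 and 10 pm, midnight, 2 and 4 am, i.e. 12. With the baseline that is 13 per day, and 2 x 13 = 26, as stated. From 3 pm to 4 am is 13 h, although section 2.5 calls it 12 h; sections 2.4 and 2.5 should be reconciled. A window ending at 6 pm keeps 7 post-dose samples and drops 5.

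**The plan's own figure.** Effect size 0.22/0.28 = 0.786. For a two-sided paired t-test at 0.05, power is 0.776 at n = 14, 0.808 at n = 15 and 0.836 at n = 16. The sample size of 16 is reproduced. It treats 0.28 mM as the SD of the analysed difference; section 7.1 describes it only as the SD of an untreated difference between the two days, not as the SD of delta Max.

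**Size of the maximum's bias.** Let s be the within-day noise SD (not in the protocol; assumed 0.05 to 0.198, the top value being 0.28/√2). For 12 independent normal samples the expected maximum is 1.63 s. Placebo-day delta Max with no true rise therefore averages 0.08, 0.16 and 0.32 mM for s = 0.05, 0.10 and 0.198.

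Suppose a large rise lifts three samples equally. The expected maximum of three is 3/(2√π) = 0.85 s, so the contrast is off by about (0.85 − 1.63) s = −0.78 s: −0.04, −0.08 and −0.15 mM.

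**Simulation on the actual sampling times.** Assumed: additive noise, hourly correlation 0 or 0.7, a rise built from six hourly boluses with half-life 1 to 4 h. Mean of the paired contrast:

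| s (mM) | true peak 0.22 | true peak 0.44 |
|---|---|---|
| 0.05 | 0.16–0.18 | 0.37–0.40 |
| 0.10 | 0.14–0.16 | 0.32–0.37 |
| 0.198 | 0.11–0.14 | 0.27–0.32 |

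With 15–70% of the variance within the day, hourly correlation 0.7 and response SD 0.15, a true 0.22 averages about 0.13–0.18 over the whole day and 0.16–0.20 when both days stop at 6 pm. The window recovers part of the shortfall, not all of it.

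**When the bias is absent or reversed.** A flat rise over all 12 samples gives 0.22, with no bias. With noise proportional to level (baseline 0.1–0.4 mM, CV 20–40%, half-life 1 to 4 h) the contrast averages 0.19–0.28 for a true 0.22, so it can overstate.

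**Baseline.** Let f be the share of single-value variance common to all samples of a day, and v the variance of the maximum relative to single-sample noise. Apart from a common factor, the contrast variance is f + (1 − f)v without baseline subtraction and (1 − f)v + (1 − f) with it. These are equal at f = 1 − f, i.e. f = 0.5. Simulated SDs (single-value SD 0.198, half-life 2 h, independent noise, no between-patient response variation):

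| f | with subtraction | without |
|---|---|---|
| 0 | 0.325 | 0.164 |
| 0.25 | 0.282 | 0.200 |
| 0.50 | 0.230 | 0.229 |
| 0.75 | 0.164 | 0.256 |
| 0.90 | 0.105 | 0.272 |

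At f = 0 the baselines supply 1 − 0.164²/0.325² = 75% of the variance. At f = 0.75 subtraction clearly helps.

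**Power against zero, true peak 0.22, n = 16.** At f = 0: mean 0.126, SD 0.325, power 0.31. At f = 0.75: mean 0.146, SD 0.164, power 0.92. The planned 0.836 lies between.

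**The case against.** A reader might infer that the primary contrast is certain to understate the rise and to be less precise. The documents do not support that. They give no within-day variance, no correlation between samples and no statement that noise is additive. The direction of the bias depends on the last of these and on how long the rise lasts, and subtracting the baseline gains precision once more than half of the variance is shared within a day. A reader might also take 0.28 mM as the SD of a difference between two single samples; section 7.1 does not say so. These objections stand, and they limit the point to what can happen.

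The 6 pm cut-off is also open to challenge. Section 1 reports slower 3-hydroxybutyrate clearance in septic mice and a second conversion step in the liver, and section 2.4 admits patients who are not being fed, for whom the evening feeding stop has no meaning. When the time of the peak is unknown, a maximum over all samples is a defensible choice. In one slow-uptake check the window left the mean at 0.157 (70% of variance within the day) or moved it only from 0.174 to 0.178 (15%). This stands as a reason to keep the whole-day maximum alongside.

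It can be said that the second primary variable, time at least 0.22 mmol/l above baseline, and the AUC already cover the matter. They help description, but neither is in mM, so neither can be set against the 0.22 mM limit in section 7.1, and the time variable depends on the same baseline. Finally, windows and covariates are often left to a SAP. Here, though, the protocol itself defines the variable and its test, and the point concerns that definition.

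**Conclusion.** The point holds in conditional form. As defined, delta Max can understate the rise: by about 0.04 to 0.09 mM for a true 0.22 (0.22 − 0.18 and 0.22 − 0.13), and up to 0.11 mM in the noisiest settings. This requires roughly additive noise and a rise confined to part of the day. It is nil for a sustained rise and can change sign under proportional noise. The single baseline costs precision only if a large part of the variance arises within the day. All sizes rest on assumed noise inputs.

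The changes should not be oversold. The requirement that the lower limit exceed 0.22 mM is demanding for other reasons: at a true 0.22 an unbiased estimate passes with probability 0.025, and no window alters that. The gain appears at larger effects. For a true rise of 0.50, in the simulation with 15–70% of variance within the day, the chance of passing goes from 45–99% as written to 73–100% with both changes. This is a cheap improvement to the primary estimate, not an error that invalidates the design.

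**What to change.** In Protocol section 7.2:

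(a) Analyse the within-patient difference in delta Max (3HHB day minus placebo day) with the difference between the two days' pre-dose values as covariate, and report the effect at equal baselines with its 95% CI. The data then set the weight of the baseline instead of fixing it at 1. Under the assumptions above the interval is up to about 15% narrower and at worst 2–3% wider. The cost is one degree of freedom. State how this fits with the transformation and non-parametric fallback, since the 0.22 limit is in mM.

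(b) Prespecify the same dosing-related window for the maximum on both days, for example 11 am to 6 pm, and keep the whole-day maximum as a secondary or sensitivity parameter. The cost is that a peak after the window is seen only in the secondary parameter, and only part of the bias is removed.

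Both are wording changes; every sample needed is already scheduled. If the prior ICU data behind the 0.28 mM include serial samples, the within-day variance should be read from them before the window is fixed, and it should be stated whether 0.28 mM applies to delta Max.
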